6. STATISTICAL CONSIDERATIONS

At the Heart Center ICU, Rigshospitalet, 20-40 patients with HF is admitted monthly from this patient population, 5-10 will require Swan Ganz monitoring and will eligible for the present study.

Around 30 patients have a CardioMEMS sensor implanted and are followed at the out-patient HF clinic at Rigshospitalet.

For this pilot study, we estimate that 15 patients in the ICU part and 10 patients in the out-patient part will be sufficient to evaluate the feasibility of the ReDs systems.

7. PARTICIPANTS

ICU part

Inclusion criteria:

- at least 18 years of age
- hospitalized in ICU setting at Rigshospitalet
- intubated
- unconscious or sedated (Glasgow Coma Score <8)
- monitored using Swan-Ganz and arterial catheterization.

Exclusion criteria:

- pacemaker or ICD

- congenital heart malformations or intra-thoracic mass that would affect the right lung anatomy (e.g. dextrocardia, lung carcinoma)
- wounds, burns, healing tissue, skin infection or recent skin graft or flap where the sensors should be attached to the skin
- habitus is out of range due to one or more of the following
 - height less than 155 cm or higher than 195 cm
 - estimated BMI of less than 22 or more than 36
 - standard active therapy has been stopped as the patient is inevitably dying.

Out-patient part

Inclusion criteria:

- 1) at least 18 years of age
- 2) history of Chronic heart failure > 3 months
- 3) CardioMEMS

Exclusion criteria:

- 1) pacemaker or ICD on the right side
- 2) congenital heart malformations or intra-thoracic mass that would affect the right lung anatomy (e.g. dextrocardia, lung carcinoma)
- 3) wounds, burns, healing tissue, skin infection or recent skin graft or flap where the sensors should be attached to the skin
- 4) habitus is out of range due to one or more of the following
 - a. Height less than 155 cm or higher than 195 cm
 - b. BMI of less than 22 or more than 38
 - i. For BMI 36 to 38, chest size ruler should be 39 or less
- 5) cancer or other severe non-cardiac disease with estimated life expectancy less than 1 year
- 6) planned hospitalization for ICD, pacemaker, lung or heart surgery including heart transplantation during the study period.

8. RISKS, SIDE EFFECTS AND SHORT-TERM AND LONG-TERM INCONVENIENCES

The ReDS System will be used in accordance with the manufacturers instruction and be operated by trained healthcare workers. Operator will be monitoring patients' skin for any side effects of sensor interaction like redness. Sensors will be removed if any sensor interaction is observed. No additional risks and long-term inconveniences are expected. However, unknown side effects or risks associated with the study program cannot be ruled-out.

9. BIOLOGICAL MATERIAL

No biological material will be collected in the study.

10. DATA FROM MEDICAL JOURNALS

The following data will be collected from medical records after informed consent:

ICU part

- 1) Patients demographics
- 2) Contact information
- 3) Comorbidities
- 4) Actual medical therapy
- 5) ECG monitoring (HR, arrhythmias)
- 6) Standard biochemistry (including hemoglobin, creatinine, BNP, electrolytes)
- 7) Systolic, diastolic and mean arterial pressure from arterial catheter
- 8) Urine output
- 9) Time and dose of all vasoactive and diuretic
- 10) Fluid administration
- 11) Dialysis
- 12) Netto fluid in/output.
- 13) Central venous pressure
- 14) Swan Ganz measurements: dPAP, mPAP, CO, CI, PAWP.
- 15) Changes in respiratory ventilation settings
- 16) Saturation from periphery pulse oximetry
- 17) Central venous oxygenation
- 18) Transthoracic echocardiography for evaluation of LVEF.

Out-patient part

- 1) Patients age
- 2) Comorbidities (only recorded at first visit)
- 3) Actual medical therapy
- 4) Hospitalization the past 90 days including diagnosis
- 5) CardioMEMS measures

11. HANDLING OF PERSONAL DATA

All data is processed and stored confidentially, and personal data will always be handled in accordance with the Danish Data Protection Act and the General Data Protection Regulation. Source data will be recorded in the electronic patient record or on specific worksheets. Fluid parameters in the ReDS systems are stored pseudo-anonymously on the device and are then moved to a secure database (Loggede Data). The ReDS-systems will be kept offline and therefore the ReDS reading will not be sent to a cloud as indicated in the instruction for use (02.02b). The ReDS systems are stored in a locked and secure room at Rigshospitalet. An electronic Case Report Form (eCRF) will be constructed for data capture. Data are stored pseudo-anonymously in a separate approved and secure database (Capital Region RedCap), which only the doctors, research assistants and project nurses of the trial will access using person-specific log-in and password. A study id is used as patient identification in the RedCap database. The key linking the study-id with the personal id is kept separately from the study data with limited access controlled by the study investigator or designee. Authority and obligations are documented in the log of delegation of responsibility in the trial. The

investigators are responsible for ensuring the accuracy, completeness, legibility and timeliness of the data recorded in the eCRFs.

The informed consent gives the investigator and possibly control authority direct access to data from the patient's journal. These are used to view information on the participant's medical condition necessary for the conduct of the trial and for self-control, quality control and monitoring. The data can be used for supplementary scientific purposes, educational purposes and publication.

The trial will be reported to the Knowledge Centre on Data Protection Compliance in the Capital Region and will not be initiated before it is approved. The study database will be maintained for 10 years after completion of the study after which the data will be deleted.

12. ECONOMY

The project is carried out on the initiative of [name]. The study is independent of commercial interests and external sponsors will have no influence on the conduct of the study. The investigators have no financial or other connection with the granting authority or Sensible Medical.

13. COMPENSATION TO PARTICIPANTS

Reimbursement will not be given.

14. RECRUITMENT OF PARTICIPANTS AND INFORMED CONSENT

For the ICU part, eligible patients are unconscious and accordingly not able to provide informed consent. Therefore, informed content will be obtained from an independent guardian and a close relative according to Medical Device Regulation (MDR) article 64. The independent guardian will be a physician at Rigshospitalet without treatment responsibility for the patient. The guardian will be independent of the investigator's interest and without interest in the study. Based on all available knowledge of the patient and the study, the guardian will decide whether it is justifiable for the patient to participate in the study.

Informed consent will be obtained from the nearest relatives in accordance with MDR article 64 prior to patient inclusion. The first contact to the nearest relatives will be at the ICU department or by telephone if the relatives have already informed the ICU department that they are not planning to visit the patient within the next 12 hours. Before the study information is presented to the relatives, they will be informed that it is an inquiry about participation in a medical health science project from the treating team at the ICU. The relatives will be informed that they can bring an assessor. Further, they will be informed that they will be given the time needed for consideration before signing the informed consent following the meeting. The information will be provided in a quiet, designated room close to the ICU department. The information is given by a doctor from the ICU department or by the investigators or designee. The nearest relatives will be given written and oral information about the study and encouraged to ask questions. The relatives or the patient will be informed of the possibility of receiving information about the study results and new health information and the possibility of declining this on the informed consent. As this part of the study is in unconscious patients, the usual 24 hours considerations time will be shorter, if and only if the relatives accept. This is due to logistical issues otherwise difficult to accomplish in the short time window of one to two days where the patient fulfilled the inclusion and none of the exclusion criteria. A minimum of 3 hours considerations time will be given.

Patients are informed that the document "Participants rights in health research projects" are enclosed with the written information.

If a patient regains before initiation of monitoring, they no longer fulfill the inclusion criteria and are no longer a candidate for the study. If the patient regains consciousness following the end of the monitoring period, they will be asked for informed consent and participant information. If patients are not interested in participation all data recorded will be deleted.

For the out-patient part, potentially eligible participants will be identified during planned outpatient appointments in the HF clinic by the treating HF specialist. The treating HF specialist will ask if the patient would like to have more information on the study. If the patient is interested, the patient will receive the written participant information and "Participants rights in health research projects". The investigator or delegate will then contact the patient either at the hospital or over the telephone to arrange a meeting with the patient. The patient will be informed of the right to bring an assessor and 24-hour deliberation time. The assessor can be present physically or electronically through audio/video connection. At the meeting the investigator or delegate will provide information about the study after which the participant has a minimum of 24 hours to consider their participation. If needed, a meeting will be for signing the informed consent.

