The manufacturer of the above investigational device hereby confirms that the investigational device in question is based on the CE marked device (ReDS Pro System V2.7), using the same bedside console configuration which includes main electronics, power components and software. The main modification includes replacing the applied non-contact sensors used for spot measurements, with slim skin-patches sensors design which are single-patient-use and utilized for monitoring patients inside the ICU under the supervision of a trained professional during an observational study. An assessment of the safety implications of the modifications has been performed. Instructions for use and testing were adapted accordingly. Hence, device modifications related to the clinical study in the ICU do not raise any issue of electrical safety or biocompatibility. Other risks specific for the use in ICU will be monitored, assessed, and reported in accordance with GCP requirements. The manufacturer declares that the noted device is safe for use as an investigational device in an observational clinical study in Rigshospitalet Hospital, Copenhagen, Denmark. For detailed comparison to the CE marked device see investigator brochure.

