We hypothesize that ReDS 2.7 allows for the identification of pulmonary congestion in out-patients before they develop symptomatic HF exacerbation and that the measurements are correlated with the CardioMEMS measurements. The aim of the out-patient part of the trial is to evaluate ReDS V2.7 efficacy in measuring lung fluid compared to pulmonary artery pressure guided therapy (CardioMEMS) in HF patients in the outpatient clinic under article 82 of the medical device regulation. The CardioMEMS HF System is CE marked and currently used in clinical practice at specialized hospitals in Denmark in patients with HF and NYHA functional class III.

We hypothesize that ReDS ICU allows for hemodynamic monitoring of ICU-patients continuously and that ReDS ICU provides hemodynamic measurements that are highly correlated with the Swan-Ganz measurements. We expect that changes to upper body-position will not affect the fluid parameter measured by ReDS ICU while the raised leg test, which increases the preload, will increase the fluid parameter measured by ReDS ICU. The aim of the ICU-patient part of the trial is to evaluate the feasibility of ReDS ICU system in critical-ill patients in an ICU setting under article 82 of the medical device regulation.

ReDS Pro System V2.7 and ReDS ICU are the same system, as described in the investigators brochure with only minor modifications (Appendix 02.02b). For the ReDS Pro System V.2.7, we will conduct an investigator-initiated study of already CE approved medical advice and for the ReDS ICU System we will test this prototype without the intention of obtaining CE-approval.

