In the out-patient part, if the patient is eligible and provides informed consent, the patient will have 4 measurements of lung fluid, which will be done as home-visits by a study designated healthcare worker. The first visit will be after inclusion and the following visits will be 14 (+/-5) days, 28 (+/-5) days and 42 (+/-5) days after the first visit.

The visits are expected to take no more than 1 hour each. During each visit the following data will be recorded:

- 1) Height (only recorded at first visit) and weight (recorded each visit)
- 2) NYHA functional class
- 3) Presence of peripheral oedema
- 4) Orthopnea
- 5) Rales by auscultation
- 6) CardioMEMS measures
- 7) ReDS v2.7 measures lung fluid parameter

Endpoints

Primary endpoints

ICU part:

- Correlation between ReDS ICU fluid parameters and Swan-Ganz measurements including right atrial pressure, pulmonary wedge pressure, mPAP and dPAP.

Out-patient part:

- Correlation between ReDS v2.7 fluid parameters and CardioMEMS measurements

Secondary endpoints

ICU part

- Changes in ReDS ICU fluid parameters following changes in Positive End Expiratory Pressure.
- Changes in ReDS ICU fluid parameters following raised leg test.
- Changes in ReDS ICU fluid parameters following changes in body position.
- Changes in ReDS ICU fluid parameters following changes administration of diuretics and inotropic/inodilators

Out-patient part

- Correlation between ReDS v2.7 fluid parameters and body weight
- Correlation between ReDS v2.7 fluid parameters and CardioMEMs measure
- Correlation between ReDS v2.7 fluid parameters and dyspnea symptom evaluated by NYHA class.

SAFETY

Safety assessments will consist of registration and recording of adverse events (AEs), adverse device effects (ADEs), Serious Adverse Events (SAEs) and Serious Adverse Device Effects (SADEs). AEs, ADEs, SAEs and SADEs will be recorded during ReDS Pro System v2.7 and ReDS ICU monitoring time.

The following adverse device events (ADE) can be expected from both devices: Localized rash and redness of the skin.

Regarding, SAEs: The population of interest is vulnerable, and hospitalizations, prolonged ICU stay (ICU part), changes to medical therapy and death are considered likely.

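### Does deleting all data of an ICU patient who later declines conflict with the protocol's safety recording?

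*Protocol*

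**What the plan says.** Section 14 explains that in the ICU part "eligible patients are unconscious and accordingly not able to provide informed consent". An independent guardian and the nearest relatives therefore consent first. The patient's own turn comes later: "If the patient regains consciousness following the end of the monitoring period, they will be asked for informed consent and participant information". The rule on refusal follows at once: "If patients are not interested in participation all data recorded will be deleted". It names no type of data and makes no exception.

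Two other places deal with safety information. Section 5, under Safety, states that "AEs, ADEs, SAEs and SADEs will be recorded during ReDS Pro System v2.7 and ReDS ICU monitoring time". In Section 3, the manufacturer's statement for the ICU device states that "Other risks specific for the use in ICU will be monitored, assessed, and reported in accordance with GCP requirements".

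Section 11 allows source data to be entered in the electronic patient record or on study worksheets, and keeps the study database for 10 years. It does not mention safety records of patients who decline.

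**The concern.** Recording events is the whole of the protocol's stated safety assessment, and the ICU configuration is the less tested of the two. Section 4 says that "for the ReDS ICU System we will test this prototype without the intention of obtaining CE-approval", and Section 5 has it worn for 48 hours. An event during monitoring is already recorded when a patient is asked for consent afterwards, so a rule that deletes everything would appear to delete that event too.

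The loss would also depend on outcome. Only patients who wake can decline, and Section 14 sets no deletion for those who die or never wake. Section 5 says of this population that "changes to medical therapy and death are considered likely". The patients left in the safety summary could therefore differ from all those who wore the device, and the number exposed might become unclear. If the only device effect fell in a single decliner, the study would count 0 of 14 where 1 of 15 had occurred. Deleted records cannot be restored by a later analysis plan.

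**Working it through.** The protocol gives no figure on this point, so the main check sets the rules beside each other in order of time.

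1. **During the 48 hours.** Section 5 requires events to be recorded in the monitoring period. The refusal rule cannot yet apply, because Section 14 triggers it only after monitoring has ended and the patient has woken and been asked. The recording duty can be met in full.
2. **When an event occurs.** Section 3 promises monitoring, assessment and reporting. A report made at the time meets this promise, and deleting study data later does not undo it. An event not yet reported at the time of refusal is the one case left unsettled.
3. **After a refusal.** Section 14 deletes what was recorded. Neither Section 3 nor Section 5 says that records stay in the study data after a refusal. The 10-year period in Section 11 concerns the database as a whole and is not worded as an exception to Section 14.
4. **What the deletion reaches.** Section 11 places some source data in the electronic patient record. Section 14 does not say that deletion extends there, so a clinical entry may survive.

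All the rules can therefore be followed in sequence. What is missing is a statement of whether safety records and the count of exposed patients fall under the deletion.

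**Size.** The planned ICU sample is 15 (Sections 5 and 6). Each refusal removes 1/15 = 6.7% of it. Section 5 says that patients who withdraw are not replaced, and does not say whether a later decliner counts as withdrawn. The documents give no rate of waking or refusal, so the numbers of decliners below are assumptions. With no device effect in the remaining n patients, the one-sided 95% upper limit for its rate is 1 − 0.05^(1/n):

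| Assumed decliners | n left | Upper limit |
|---|---|---|
| 0 | 15 | 1 − 0.05^(1/15) = 18.1% |
| 1 | 14 | 1 − 0.05^(1/14) = 19.3% |
| 3 | 12 | 1 − 0.05^(1/12) = 22.1% |
| 5 | 10 | 1 − 0.05^(1/10) = 25.9% |

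The protocol plans no such limit, so the table only gives scale. Even with nobody declining, 15 patients cannot exclude a device-effect rate of 18%. One refusal moves the limit by 19.3 − 18.1 = 1.2 percentage points.

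**Effect on the planned analyses.** The ICU endpoints in Section 5 are correlations with Swan-Ganz measurements and changes in the fluid parameter after tests and drugs. Section 6 justifies the sample by feasibility. None of these analyses uses adverse-event records. Deleting the measurement data of a decliner does reduce the endpoint data, but that is an accepted consequence of a refusal.

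**The case for a change.** The strongest case for a change is that the sentence in Section 14 has no exception, that deletion is irreversible, and that a few words would settle the matter before the first refusal. Recording an event only to erase it leaves the recording with little use. Every ICU patient who wakes after monitoring reaches this step, since all enter without being able to consent. Section 5 lists rash and redness as expected device effects, and Section 8 concedes that unknown risks cannot be ruled out.

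Much of this stands. The wording is silent, and on a literal reading the study's safety data would lack a decliner's events. Three parts do not carry a change:

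- Reaching the question is not the same as declining. Nothing in the documents shows that refusal is common, and the relatives and a guardian have already agreed.
- The selection by outcome is plausible, but neither its direction nor its size can be derived. Section 14 also does not promise that the data of all other patients are kept, and Section 5 allows withdrawal on medical grounds.
- Any clarification could go either way. Keeping safety records gives a complete account of exposure but retains data on someone who refused. Deleting them respects the refusal but leaves a gap. That choice turns on consent law, ethics approval and participant information that are not in the document at hand, and no statistical argument makes one answer right.

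Section 14 also does not say what happens if a patient wakes during monitoring. That is a detail of the consent procedure, and it creates no conflict with the safety sections.

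**Conclusion.** No change to the plan follows. Section 14 is silent on whether its deletion covers safety records and the count of exposed patients. It does not strictly contradict Sections 3 and 5, because recording and reporting precede any refusal and neither section promises retention after one. Full deletion on refusal is a defensible choice for patients enrolled while unable to consent.

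The cost is at most 1 of 15 patients (6.7%) per refusal in a safety summary with no planned estimate, and it touches no endpoint analysis through the safety records. A sensible report would give the number of patients who declined and say that the safety summary excludes them. A bare count identifies nobody.

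This rests on two assumptions: that events are reported when they occur, before any refusal, and that entries in the patient record are not erased. If either failed, a device effect in a decliner could be lost altogether. The documents do not indicate that either would fail.

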15. PUBLICATION

Results, positive, negative, or inconclusive, will be published in international medical journals. The trial will be registered at <https://clinicaltrials.gov>. Additionally, the results will be presented at national and international congresses. The participants will not be identifiable in any reports or publications.

16. ETHICAL CONSIDERATIONS

This clinical trial complies with the Declaration of Helsinki, modified by the 64th World Congress in Fortaleza, Brazil in 2013.

The planned examinations in outpatient-part and ICU-part are all considered very low-risk procedures. All planned examinations in the ICU part, except for the fluid parameter measures from the ReDS system, are part of the routine work-up of patients in an ICU setting. The planned experimental design with different body positions during ICU care is considered very low risk with no expectation of harm or long-term inconveniences. All planned examinations in the out-patient part except for the ReDS fluid parameter are all standard HF care. The CardioMEMS sensor is CE marked and currently used in clinical practice in selected patients with chronic HF. The ReDS system is CE marked for the out-patient fluid parameter measures.

The participants are not expected to benefit directly from their participation in the study. The knowledge obtained by this study may contribute to a future reduction in hospitalizations for chronic HF patients by the non-invasive use of the ReDS system. If the ReDS ICU systems proves feasible in an ICU setting, this could help guide physicians for treatment of the critical-ill patients and hopefully reduce the length of stay at the ICU and mortality. We believe that the potential gain from the studies is greater than the risks that the participants are exposed to.

